Eligibility criteria

The sample will be open to HIV-infected men and women aged 18-60 years of all racial/ethnic groups who are currently on antiretroviral medications for >3 months and are cocaine users. Cocaine use will be defined as lifetime regular crack/cocaine use lasting >1 year, cocaine-type stimulant use disorder, and cocaine as the principal substance of abuse. Exclusion criteria will include pregnancy; English non-fluency or illiteracy; ≤ 8th grade education; serious and unstable neurological disorders; unstable serious mental illness or acute psychiatric distress; and impaired mental status. Women who are pregnant will be excluded because of the known effects of pregnancy on neuropsychological functioning (including deficits in memory and executive control). To reduce potential attrition, individuals who state they are planning to move away from the area within the next 3 months and individuals without stable housing will be excluded.

Recruitment

Both clinic- and community-based recruitment strategies will be used. Participants will learn about the study via flyers in clinics, community-based organizations that serve HIV-positive individuals, and participant referrals. Clinic recruitment will occur at local infectious diseases clinics. Patients may also self-refer in response to flyers and brochures displayed in the waiting

area and exam rooms. We may also run advertisements in local newspapers and online. Finally, participants may be recruited through our lab's repository contact database (IRB Pro00047043).

Prescreening

Regardless of how potential participants are informed of the study, interested individuals will complete a pre-screening with a member of the research staff to determine preliminary eligibility. This pre-screening will occur in person or over the telephone.

Cognitive Training Study

Screening Visit. If potentially eligible after prescreening, participants will be invited to complete a 2-3 hour screening visit in our laboratory to verify eligibility criteria. The informed consent process will occur at the beginning of this visit, followed by a breathalyzer to ensure that the participant is not acutely intoxicated. The initial part of the screening visit will include the urine drug testing and pregnancy testing if indicated. Participants will then complete questionnaires and clinical interviews to assess HIV and other medical history, substance use, and mental health (**Table 1**). Trained

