Working Memory	Paced Auditory Serial Addition Test-100 ²⁵ WAIS-IV Letter-Number Sequencing, ²² WAIS-IV Digit Span ²²
Premorbid Functioning	Wechsler Test of Adult Reading (WTAR) ²⁶
Decision Making	
Decision Making	Game of Dice Task ²⁷
Delay discounting	Monetary Choice Questionnaire ²⁸
Abstract reasoning	Wisconsin Card Sorting Test-64 (WCST) ²⁹
ACASI	
Psychiatric Symptoms	Symptom Checklist 90-Revised (SCL-90) ⁶
Food Insecurity	Household Food Insecurity Access Scale ³⁰
Craving	Stimulant Craving ⁹
Quality of Life	World Health Organization Quality of Life-BREF (WHOQOL-BREF) ³¹
Self-assessment	Patient's Assessment of Own Functioning Inventory ³²
Sexual/Drug Risk	Risk Assessment Battery (RAB) ³³
Nicotine Dependence	Fagerstrom Test for Nicotine Dependence (FTND) ³⁴ and smoking history
Stimulant Dependence	Severity of Dependence Scale (SDS) ³⁵

selections will be analyzed. The Monetary-Choice Questionnaire (MCQ) is a delay discounting task. Participants make 36 choices between smaller immediate rewards (ranging from \$11 to \$78) and larger delayed rewards (ranging from \$25 to \$85 and from 7 to 186 days). An individual's point of indifference where the perceived value of a smaller immediate reward is equivalent to a larger delayed reward is computed using the following hyperbolic function: $V_{\text{immediate}} = V_{\text{delayed}} / (1 + kD)$, in which V is value in dollars, D is delay in days, and k is a free parameter that determines the discount rate. The Wisconsin Card Sorting Test-64 (WCST) is used to measure abstract reasoning, concept generation, and perseverative responding. In this computerized task, participants sort cards according to one of three principles of class membership, including categories completed, perseverative responses, perseverative errors, nonperseverative errors, failure to maintain set, and efficiency of learning.

Cognitive Training Sessions. At the end of the baseline assessment, enrolled participants will be randomly assigned to either the experimental (Active Cognitive Training, or ACT) or control (or CON) conditions using simple random assignment. Participants will be trained to use Lumosity after the baseline assessment. Research staff will provide instructions and guide them through the first training session. Participants will then immediately begin completing sessions at home the following day.

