Schedule of training sessions. All enrolled participants will be asked to complete 48 training sessions over 10 weeks. The sessions will last approximately 20-30 minutes and will be completed at home or wherever the participant can obtain computer access. If the participant has no means of accessing a computer, sessions can be completed in-person in the research laboratory. Participants will be encouraged to complete 6 sessions a week, 1 per day, to reach a total of 48 by the end of the 10-week period. While each group will complete the same number of sessions to control for possible dosage effects, the content of the sessions will vary by study group. Each condition will include 8 unique Lumosity games.

Active Cognitive Training (ACT). Sessions will include games from Lumosity that are designated as targeting working memory. One training session will be comprised of a randomly generated subset of 4 of the 8 working memory games, each played twice back-to-back.

Control Training (CON). The sessions will be in the same format as the ACT group, but will utilize other Lumosity games that do not target working memory. These games will be the same length as the working memory games and participants will complete the same number of randomly generated games per session (4 of the 8 games, played twice back-to-back).

Post-training Assessment. After completing the 48th training session, or at the end of the 10-week training window, participants will complete a post-training assessment. This 3-hour visit will occur within 1 week of the final training session and will consist of a battery identical to the baseline assessment. Alternate forms of neuropsychological tests involving memory will be used to avoid effects related to repeated testing. Participants will also complete a process measure to describe their experiences of the intervention and provide feedback on perceived benefits, barriers to completing sessions, and the length, number, and content of sessions. This assessment includes open-ended questions and ratings of satisfaction and helpfulness.

One-month Follow-up Assessment. One month after the post-training assessment, participants will complete a follow-up assessment. This 3-hour visit will consist of a battery identical to the baseline assessment. Alternate forms of neuropsychological tests involving memory will be used to avoid any effects related to repeated testing.

Human Subjects Protections

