Initial analyses will confirm the psychometric properties of the assessments, and scale scores will be constructed. Data distributions will be checked to determine if they meet the assumptions of the analytic models, and transformations will be performed when necessary to improve distributional qualities. Preliminary analyses will compare study groups on demographic and other characteristics obtained in the screening and baseline assessments to identify possible failures in random assignment, which would be statistically controlled for in subsequent analyses. We will also test for any differential attrition across groups at both follow-ups. All analyses will be repeated with other substance use added as a covariate.

Hypothesis testing (Aim 1). Using an intent-to-treat analysis, we will investigate the differential impact of condition (ACT vs. CON) at the post-training assessment by performing a 2 (Condition) by 2 (Time) general linear model (GLM) analysis on the main outcome measures of working memory (mean T-score on the 3-test battery) and delay discounting (natural log k-value). Time will be a within subjects factor defined by baseline versus post-training assessment. The analysis will be repeated, adding the 1-month follow-up in a 2 (Condition) by 3 (Time) GLM to detect differential effects of the two conditions on outcomes through the follow-up period. Significant interactions of Condition and Time are predicted. To examine the specificity of the cognitive training intervention, we will use the same models to test for group differences on performance in other cognitive domains (e.g., verbal fluency, processing speed) and other measures of decision making (i.e., contingency learning, risk taking propensity).

Additional analyses will be restricted to participants who were randomized to ACT. First, we will examine predictors of treatment response (moderators) based on sample characteristics. We will use linear regression to predict change in the main outcome variables (working memory and delay discounting), with potential moderators entered separately as predictors. Second, we will use linear regression to evaluate the effect of treatment dosage (number of sessions completed) on change in the outcome variables. Finally, if intervention effects are identified on main outcomes, we will test whether effects were mediated by performance on the working memory training modules using bootstrap analyses.³⁶⁻³⁸

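### Aim 1 is labelled intent-to-treat, but the set is undefined and the 2x2 and 2x3 within-subjects GLMs have no rule for missing scores, so they can rest on different and incomplete subsets of those randomised

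*Combined protocol and SAP*

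**What the plan says.** All the relevant text is in the combined protocol and SAP.

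- **Principle and first model** (Statistical analyses, Aim 1): "Using an intent-to-treat analysis, we will investigate the differential impact of condition (ACT vs. CON) at the post-training assessment". The model is a condition-by-time GLM on the mean T-score of three working-memory tests and on the log discount rate. On the time factor: "Time will be a within subjects factor defined by baseline versus post-training assessment".
- **Second model** (same paragraph): "The analysis will be repeated, adding the 1-month follow-up in a 2 (Condition) by 3 (Time) GLM", to look at effects through the follow-up period.
- **Reuse**: "we will use the same models to test for group differences on performance in other cognitive domains" and on other decision-making measures. The Aim 3 paragraph applies the same GLMs to cocaine use, sexual risk and adherence.
- **Attrition**: the analysis section says only "We will also test for any differential attrition across groups at both follow-ups", and no action follows from that test. The eligibility section has exclusions for the same reason: "To reduce potential attrition, individuals who state they are planning to move away from the area within the next 3 months", and people without stable housing.
- **Other missing scores**: under Emotional distress, participants are told they can decline any item or procedure.
- **Non-finishers of training** (Post-training Assessment): "After completing the 48th training session, or at the end of the 10-week training window, participants will complete a post-training assessment".
- **Timing of allocation** (Cognitive Training Sessions): "At the end of the baseline assessment, enrolled participants will be randomly assigned".

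No section defines the intent-to-treat set. None gives imputation, a likelihood-based method, a missing-data sensitivity analysis, or a rule for a composite with one or two of its three tests missing.

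**The concern.** Intent-to-treat says that people are compared as assigned. It does not say how someone with no post-training score stays in a model that needs one. A within-subjects GLM, as usually fitted, needs every included visit. The label and the model therefore fit together only if nobody has a missing score, and the plan itself expects some loss.

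Three things are at stake. First, the two Aim 1 models can describe different people, so a difference between their results may reflect who was analysed and not a change over time. Second, the 2x3 discards the baseline and post-training scores of anyone who misses only the 1-month visit, which wastes information. Third, if loss is related to outcome to a different degree in the two arms, the contrast among complete cases is biased. The gap carries over to the other cognitive and decision-making outcomes and to Aim 3.

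**Working it through.** **Inputs.** The plan supplies the design: two arms, three visits, and the two GLMs. It states no sample size, attrition rate, SD or between-visit correlation, so there is no figure of its own to reproduce. The following are assumptions: unit SD at each visit, equal correlation r = 0.6-0.8 between any two visits, and 10-20% loss.

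**Step 1: who contributes.** The 2x2 interaction is a two-group comparison of change scores, so a person lacking either score adds nothing. If a share *a* is missing independently at each later visit, the 2x2 keeps 1 - a and the 2x3 keeps (1 - a)². That is 90% and 81% for a = 0.10, and 80% and 64% for a = 0.20. Skipped baseline tests would lower both shares further.

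**Step 2: random loss (no bias, only lost precision).** Per randomised participant in an arm, the variance of mean change is:

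- 2x2: 2(1 - r)/(1 - a)
- 2x3: 2(1 - r)/(1 - a)²
- Mixed model: c′I⁻¹c. Here I sums the inverse covariance of the observed visits over the four missingness patterns, with weights (1 - a)², a(1 - a), a(1 - a) and a². The covariance is treated as known.

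| a | r | Mixed | 2x2 | 2x3 | 2x2 / mixed | 2x3 / mixed |
|---|---|---|---|---|---|---|
| 0.10 | 0.6 | 0.862 | 0.889 | 0.988 | 1.03 | 1.15 |
| 0.10 | 0.8 | 0.433 | 0.444 | 0.494 | 1.03 | 1.14 |
| 0.20 | 0.6 | 0.942 | 1.000 | 1.250 | 1.06 | 1.33 |
| 0.20 | 0.8 | 0.476 | 0.500 | 0.625 | 1.05 | 1.31 |

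The ratios are the same for the post-training and 1-month contrasts from the 2x3.

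**Step 3: 1-month loss that depends on observed change.** Suppose 20% of those seen at post-training are lost before 1 month.

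- Selective loss takes half of the lowest 40% on change. The kept mean then shifts by 0.5 × 0.3863/0.8 = 0.2415 SD of change, where 0.3863 is the normal density at the 40th percentile.
- Half-selective loss takes 35% of the lowest 40% and 10% of the rest, again 20% in all. The shift is (0.35 - 0.10) × 0.3863/0.8 = 0.1207.
- The SD of change is √(2(1 - r)) = 0.894, 0.775 and 0.632 for r = 0.6, 0.7 and 0.8.
- Change to 1 month regresses on change to post-training with slope (1 - r)/(2(1 - r)) = 1/2.

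With no true effect, the bias in the 1-month contrast from the 2x3 is:

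| Loss | r = 0.6 | r = 0.7 | r = 0.8 |
|---|---|---|---|
| Selective in one arm, half as selective in the other: ½ × (0.2415 - 0.1207) × SD | 0.054 | 0.047 | 0.038 |
| Selective in one arm only: ½ × 0.2415 × SD | 0.108 | 0.094 | 0.076 |

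Simulation with 2,000,000 per arm and a further 10% random loss at post-training (72% kept) agrees to about 0.002. In the same runs the 2x2 and the mixed model are within 0.002 of zero. The sign favours the arm with the more selective loss of poor changers.

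**Step 4: loss before post-training, which can affect the 2x2.** Assume 20% loss, selective in one arm and half as selective in the other.

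- If loss depends on baseline, the 2x2 bias is -(1 - r) × 0.1207 = -0.048, -0.036 and -0.024 SD. A mixed model removes it.
- If loss depends on the unobserved change itself, the 2x2 bias is 0.1207 × SD of change = 0.108, 0.094 and 0.076. The mixed model keeps roughly (1 + r)/2 of this: 0.086, 0.079 and 0.069. It removes only about 10-20%.

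**Step 5: same mechanism in both arms.** With no true effect the two arms shift equally and the bias is zero in every model.

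**The case against.** Several points on the other side stand.

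- **Intent-to-treat already names the set.** By convention it means everyone randomised, as assigned. What is missing is an explicit definition and a way to keep people with missing scores in it.
- **Dropping incomplete cases is an inference.** A reader might conclude that the plan prescribes a complete-case analysis. It does not: it names no software and no deletion rule. The point is conditional on the usual fit of the named models.
- **Stopping training is not the problem.** A reader might infer that non-adherent participants are excluded. Those who do not finish the sessions are still assessed at the end of the 10-week window, so intent-to-treat is respected on that score.
- **The stated post-training test is little affected.** A reader might take the post-training contrast from the 2x3, where the Step 3 bias is twice the 1-month figure, as bias in the main result. The plan takes its post-training effect from the 2x2, which is unbiased in that scenario. For the 2x2, the mixed model saves only 3-6% of variance under random loss.
- **The design limits differential loss.** Control training has the same format, game length and number of sessions. Sessions can be done in the laboratory, the two later visits are paid ($65 and $85), and travel help is offered. Loss that is selective in one arm only is therefore an upper case.
- **This is a feasibility and preliminary-efficacy study.** That limits the severity, but the plan also predicts significant interactions, so the tests will be read as evidence.

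One tempting reassurance does not hold: randomisation after the baseline visit does not guarantee complete baseline scores, because any procedure may be skipped.

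**Conclusion.** The concern holds. The plan labels Aim 1 intent-to-treat without defining the set, and its two models have no rule for missing scores. Under the usual fit they can use different people, and neither need include all those randomised.

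The main cost is in the 2x3: about 1.14-1.33 times the variance of a mixed model under 10-20% random loss per visit. Its 1-month contrast is biased by about 0.04-0.05 SD when 20% loss depends on observed change and is half as selective in one arm. The figure is 0.08-0.11 SD if loss is selective in one arm only. If the T-score SD is 10 (an assumption), these are about 0.4-0.5 and 0.8-1.1 points. All of these sizes rest on the assumed loss rates, selection rules and r = 0.6-0.8.

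A reader might infer that bias is inevitable. The documents do not support that. It is zero under random loss, and also when the same mechanism acts in both arms and there is no true effect. Nor is a mixed model a complete cure, since most of the bias from loss tied to unobserved change remains. This should be corrected in the SAP and is not a fatal flaw.

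**What to change.** 1. Define the Aim 1 set as all randomised participants, by assigned arm.
2. Replace the two GLMs with one likelihood-based repeated-measures mixed model (condition, visit and condition-by-visit, with unstructured covariance) using all observed visits. Take the condition difference in change from baseline to post-training as the main contrast, and the difference in change to 1 month as the second.
3. Give a rule for a partly missing three-test composite, for example the mean of the available T-scores when at least two are present, and missing otherwise.
4. Apply the same model to the other cognitive and decision-making outcomes and, where its assumptions fit, to Aim 3.
5. Optionally, add a simple not-missing-at-random sensitivity analysis, such as shifting the unobserved scores by a range of fixed amounts by arm.

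Keeping the GLMs with multiple imputation is an acceptable alternative. If they are kept without imputation, describe the result as complete-case by assigned arm and not as intent-to-treat.

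The cost is SAP wording and slightly more analysis work in standard software. It needs no extra data, visits or participants.

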COGNITIVE TRAINING TO REDUCE IMPULSIVITY IN HIV-INFECTED COCAINE USERS

NCT02909101

Study Protocol with Statistical Analysis Plan

VERSION DATE: April 13, 2018

Specific Aims

This study tests the feasibility and preliminary efficacy of a computerized cognitive training program to improve working memory and decrease impulsivity (delay discounting) among HIV-infected individuals. The specific aims are to

- (1) Investigate the effects of the cognitive training intervention on working memory (primary outcome) and delay discounting (secondary outcome) in HIV-infected persons;
- (2) Establish the acceptability of computerized cognitive training among HIV-infected past or present cocaine users; and
- (3) Examine the effect of cognitive training on HIV risk behaviors, including cocaine use, risky sex, and medication adherence (exploratory outcomes).

We hypothesize that: (1) Participants assigned to active cognitive training (ACT), compared to those in the attention-matched control group (CON), will have greater improvements in working memory and reductions in delay discounting; (2) Participants assigned to ACT, compared to those in CON, will have greater reductions in HIV risk behaviors, including improvements in medication adherence.

Study design

The proposed study will test the efficacy of a cognitive training program to improve working memory in a sample of HIV-infected cocaine users. We will evaluate the effects of this cognitive training intervention on working memory, delay discounting, and HIV risk behaviors. We will first screen participants for eligibility. Eligible participants will be assigned to one of two groups (ACT or CON) and will complete 48 training sessions over 10 weeks. Participants assigned to ACT will complete computerized games designed to enhance working memory, while those assigned to the attention-matched CON will complete games that use other brain attributes. We will be using a web-based program, Lumosity (Lumos Labs, Inc.; <http://www.lumosity.com>). Lumosity is available to the public and offers user-friendly cognitive training games targeting different brain areas. We have developed a contract with Lumosity tailoring the website to fit our study's needs. All participants will complete assessments at baseline, post-training, and 1-month follow-up to evaluate the impact of the training program. Staff members conducting assessments will be blinded to treatment condition in order to ensure no biases occur during testing.

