Acceptability (Aim 2). We will examine participant ratings of satisfaction with the cognitive training intervention, as well as their perception of its benefits and barriers to completing sessions. The intervention will be considered acceptable if participant ratings are high (>3.5 on a 5-point scale). We will also calculate the average number of sessions completed and determine the proportion of participants who successfully completed the intervention (defined as completing ≥36 of the 48 total sessions). The intervention will be considered acceptable to the target population if ≥80% complete the intervention.

Exploratory analyses (Aim 3): To investigate the impact of the intervention on risk behaviors, we will use the same GLM models described above to test for differences by condition on cocaine use (number of days of use), sexual risk (HRBS sex risk score), and adherence to ARVs (percent medication adherence).

Clinical Trials Registration

This study is registered at <http://www.ClinicalTrials.gov> (Identifier: NCT: NCT02909101).

References

4. RAND Corporation. *HIV Cost and Services Utilization Study (HCSUS) baseline questionnaire*. Santa Monica, CA: RAND Corporation; 2007.
5. Wilkinson GS, Robertson GJ. *Wide Range Achievement Test-4 (WRAT-4)*. Lutz, FL: Psychological Assessment Resources.
6. Derogatis LR. *Brief Symptom Inventory: Administration, Scoring, and Procedures Manual*. 3rd ed. Minneapolis, MN: National Computer Systems, Inc.; 1993.

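### The primary 2×2 Condition × Time test is a valid change-score comparison, but pre-specified adjustment for the baseline score would usually be more precise at almost no cost

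*Combined protocol and SAP*

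**What the plan says.** The combined protocol and SAP, under Statistical analyses, Hypothesis testing (Aim 1), specifies "performing a 2 (Condition) by 2 (Time) general linear model (GLM) analysis on the main outcome measures of working memory" and delay discounting. It adds: "Time will be a within subjects factor defined by baseline versus post-training assessment". The effect of interest is the interaction: "Significant interactions of Condition and Time are predicted". The outcomes are "working memory (mean T-score on the 3-test battery) and delay discounting (natural log k-value"; Specific Aims makes the first primary and the second secondary.

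The baseline score is therefore a repeated outcome, and nowhere a pre-specified covariate. Two other statements bear on adjustment. Preliminary analyses will compare the groups "to identify possible failures in random assignment, which would be statistically controlled for in subsequent analyses", with no criterion for what counts as a failure. All analyses will also be repeated with other substance use as a covariate.

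Cognitive Training Sessions gives the order of events: "At the end of the baseline assessment, enrolled participants will be randomly assigned to either the experimental" or control condition. The same models carry over to other cognitive domains, other decision-making measures and Aim 3, where "we will use the same GLM models described above to test for differences by condition on cocaine use" and other risk behaviours.

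**The concern.** A 2×2 model with baseline as a level of Time compares mean change between arms. That is the best use of the baseline score only when the slope of post-training on baseline score equals 1. If the slope is below 1, subtracting the whole baseline score over-corrects. It then adds noise and, after a chance imbalance, favours the arm that started lower.

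Baseline is measured before assignment, so using it as a covariate introduces no bias. What is at stake is precision on the primary outcome (working-memory mean T-score) and the secondary outcome (ln k), in a study meant to give preliminary evidence of efficacy. Type I error is not at stake.

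**Working it through.** **Inputs.** From the plan: the 2×2 model, Time as a within-subjects factor, the interaction as the test, simple randomisation after baseline. Not in the plan: N, SDs, the correlation r between baseline and post-training scores, alpha and power. Assumed here: two arms of expected equal size, two-sided alpha 0.05, r from 0.5 to 0.95, k = post SD / baseline SD of 1, 1.1 or 1.25, and total N of 20 to 100. The plan has no figure of its own to reproduce.

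**Step 1: the identity.** With two time points and complete pairs, the interaction F equals the squared t on change. Two simulated data sets confirm it: F = t² = 0.26452 in one and 2.6793 (41 df) in the other. The identity does not extend to the 2×3 model, whose interaction has 2 degrees of freedom.

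**Step 2: validity.** In simulation under no effect (N = 40 and 60, r = 0.5 to 0.9, 8,000 runs per setting), type I error was 4.6–5.4% for change scores and 4.7–5.4% for ANCOVA.

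**Step 3: large-sample variance.** In units of the baseline variance:

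- change score: 1 + k² − 2rk
- ANCOVA: k²(1 − r²)
- difference: (1 − rk)², which is never negative and is zero when rk = 1

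At k = 1 the ratio is (1 − r²)/[2(1 − r)] = (1 + r)/2. For r = 0.7, that is 0.51/0.60 = 0.85, so the change score needs 1/0.85 = 1.18 times the participants. At r = 0.5, 0.8, 0.9 and 0.95 the excess is 33%, 11%, 5% and 3%.

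**Step 4: cost of estimating the slope.** Multiply the ratio by 1 + 1/(N − 4) = (N − 3)/(N − 4). At N = 60 this is 57/56 = 1.018. ANCOVA variance / change-score variance:

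| N | k | r=0.5 | 0.7 | 0.8 | 0.9 | 0.95 |
|---|---|---|---|---|---|---|
| large | 1 | 0.750 | 0.850 | 0.900 | 0.950 | 0.975 |
| 100 | 1 | 0.758 | 0.859 | 0.909 | 0.960 | 0.985 |
| 60 | 1 | 0.763 | 0.865 | 0.916 | 0.967 | 0.992 |
| 40 | 1 | 0.771 | 0.874 | 0.925 | 0.976 | 1.002 |
| 20 | 1 | 0.797 | 0.903 | 0.956 | 1.009 | 1.036 |
| 60 | 1.1 | 0.832 | 0.938 | 0.985 | 1.017 | 1.001 |
| 60 | 1.25 | 0.909 | 0.998 | 1.018 | 0.967 | 0.827 |

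The worst case is rk = 1, where only the cost remains: 1.8% at N = 60, 2.8% at N = 40 and 6.3% at N = 20. Simulation with simple randomisation (40,000 runs per cell) gave 0.76, 0.86, 0.92, 0.97 and 1.00 at N = 60, k = 1.

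**Step 5: power at N = 60, k = 1.** This uses the noncentral t, with N − 2 df for change and N − 3 for ANCOVA, and includes the slope cost.

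| Change-score power | r=0.5 | 0.7 | 0.8 | 0.9 | 0.95 |
|---|---|---|---|---|---|
| 60% | 72% | 66% | 64% | 61% | 60% |
| 80% | 89% | 85% | 83% | 81% | 80% |

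**Step 6: does the planned imbalance check already secure this?** Suppose baseline is adjusted for only when a baseline t-test is significant at level a. In large samples the share of the gain recovered is E[Z²; |Z| > z] = a + 2zφ(z), where z is the two-sided critical value and φ the normal density:

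- a = 0.05: 0.05 + 2(1.960)(0.0584) = 0.28
- a = 0.10: 0.10 + 2(1.645)(0.1031) = 0.44
- a = 0.20: 0.20 + 2(1.282)(0.1755) = 0.65

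Simulation at N = 60, k = 1 (60,000 runs per r, r = 0.5 to 0.9) agrees: 27–32%, 43–45% and 61–66%.

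**The case against.** The strongest reply is that nothing is wrong. The model is named, the interaction matches the hypothesis of greater improvement, and the test is valid. Choosing between two valid estimators can look like preference. This stands to the extent that the point is an improvement and not a correction.

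Second, the benefit to this trial cannot be shown, because N, the SDs and r are all unstated. A mean of three tests may well have a high r. At r = 0.8 to 0.9 with equal SDs and N = 60, 80% power rises only to 83% or 81%. At r = 0.7 with k = 1.25 the gain is nil, and at N = 20 with r = 0.9 there is a 1% loss. This stands too. But the potential losses are small and capped, while the potential gains are much larger, and ANCOVA does not need r in advance.

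Third, the imbalance check may already bring in baseline working memory. It may, and a lenient criterion would recover well over half the gain. But no criterion is given, adjustment would remain conditional, and the form of the primary model would depend on the data.

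Fourth, the calculations cover only the 2×2 test. That is correct. Extending adjustment to the 1-month visit and other outcomes is for consistency and is not supported by these figures.

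**Conclusion.** The point holds as a recommended efficiency improvement. The planned 2×2 test is unbiased and controls type I error. ANCOVA targets the same effect and, apart from the (N − 3)/(N − 4) factor, is never less precise.

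Over the range examined with equal SDs and N = 60, the variance reduction runs from 24% at r = 0.5 to under 1% at r = 0.95. The gain is negligible or slightly negative when rk is near 1, or when r is very high in a very small trial. With equal SDs it disappears above r = 0.88 at N = 20, 0.95 at N = 40 and 0.96 at N = 60 (from r = 2(N − 4)/(N − 3) − 1). These sizes rest on assumed N, r, SD ratio and alpha, and on complete baseline and post-training pairs.

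**What to change.** Pre-specify the primary estimate as the ACT − CON difference in post-training working-memory mean T-score, adjusted for the baseline T-score by ANCOVA whether or not the arms differ at baseline. Do the same for ln k.

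For consistency, replace the 2×3 GLM with one repeated-measures model of the two follow-up visits, with condition, visit, condition × visit, baseline and baseline × visit. Report the post-training and 1-month contrasts from it. A mixed model with baseline means constrained equal is an alternative. The two can differ when follow-up data are missing, so name one in advance. Use baseline adjustment for the other cognitive and Aim 3 outcomes where a linear model suits their distribution.

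The cost is SAP wording and about one degree of freedom, because the baseline score is already collected. That assumes the change is made before outcomes are examined by arm, which the documents do not address.
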